6.2 Treatment Compliance

Treatment compliance will be assessed via direct observation by the study investigator who is responsible for study drug administration. The cell dose and exact time of injection will be recorded.

6.3 Supportive Care/Prohibited Treatments

Subjects will receive supportive measures as determined by their needs and according to the accepted standards of care. Subjects will be treated with ophthalmic corticosteroid eye drops to minimize any inflammation for up to 14 days starting on the day of injection, including tapering schedule. The prohibited treatments are any immunosuppressant other than topical steroids as noted above.

7.0 STUDY EVALUATIONS

7.1 Screening

- a. informed consent
- b. documentation of initial diagnosis confirmed by ERG (ERG can be performed at screening to confirm eligibility)
- c. consent to mutation typing (if not already done can be done at baseline or screening)
- d. complete medical history and physical exam, including vital signs, height, weight
- e. pregnancy test, if female
- f. blood sample for HLA typing
- g. CBC, platelet, differential, hemoglobin, hematocrit
- h. blood chemistries, not limited to, but must include AP, ALT, AST, BUN, Cr, total bilirubin, serum electrolytes, glucose, calcium, phosphate, albumin and total protein
- i. coagulation function, including PT/INR, PTT
- j. infectious disease screen (Hepatitis B and C, HIV)
- k. urinalysis, including drug screen
- l. ECG
- m. slit lamp and fundus exam
- n. BCVA

7.2 Baseline (should be within 30 days of treatment)

The assessments (indicated by an asterisk*) do not need to be repeated if Day 0 (treatment day) is within 30 days of screening. Subjects should be advised to discontinue daily aspirin or clopidogrel regimens for 5 days prior to study treatment.

- a. medical history and physical exam*, including height, weight
- b. vital signs

- c. pregnancy test, if female*
- d. hematology [CBC, platelet, differential, hemoglobin, hematocrit]*
- e. blood chemistries*, not limited to, but must include AP, ALT, AST, BUN, Cr, total bilirubin, serum electrolytes, glucose, calcium, phosphate, albumin and total protein
- f. coagulation function, including PT/INR, PTT (if abnormal at baseline, this test should be repeated each time standard safety labs, e.g. hematology and blood chemistries, are performed)*
- g. infectious disease screen* (Hepatitis B and C, HIV)
- h. urinalysis*
- i. ECG*
- j. slit lamp and fundus exam, including fundus photographs
- k. BCVA
- 1. ERG (does not need to be repeated if performed at screening to confirm eligibility)
- m. IOP
- n. OCT
- o. FA
- p. B-scan
- q. AF
- r. VF
- s. blood sample for Ab testing
- t. exploratory visual assessments, dependent upon subject's abilities

7.3 Before administration of jCell (Day 0)

- a. weight
- b. vital signs, within 15 minutes prior to injection
- c. ECG does not need to be repeated if within one week of baseline or screening ECG
- d. BCVA

7.4 After administration of a single intravitreal dose of jCell (Day 0)

- a. exact dose and time of injection; any dose interruption must be documented
- b. vital signs at 15 and 60 minutes after injection or until returned to pre-treatment levels
- c. intraocular pressure by tonometry post-treatment must be ≤30 mm Hg prior to patient release
- d. verify basic vision by lights, hand motions and fingers, depending upon individual patient's baseline prior to patient release
- e. con meds

f. adverse events

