3.1 Study Population

3.1.1 Cohort One

Up to 14 subjects will be enrolled into Cohort 1. Subjects in Cohort 1 must have BCVA no better than 20/200 and no worse than Hand Motions (HM, i.e. the patient can distinguish horizontal from vertical hand motions at 1 foot). The first four subjects in Cohort 1 will receive an intravitreal injection of 0.5 x 10^6 hRPC (50 μ L volume) into the eye with the worst visual acuity; only one eye will be injected. The procedure does not require in-patient hospitalization and can be done under topical anesthesia. Subjects will be monitored closely following injection for 60 minutes prior to being released home on the day of treatment, based on intraocular pressure <30mm Hg and vital signs returned to pre-injection. Patients will be treated with ophthalmic corticosteroid eye drops to minimize any inflammation from injection for up to 14 days (including tapering schedule). There will be a minimum four week interval between the treatment of the first and second subjects in this cohort, with follow up at 1, 2, 3, 7, 14 and 21 days post-injection by the study investigator to confirm no serious injection related AEs have occurred for subject #1 prior to treatment of subject #2. Subsequent cohort 1 subjects at the same dose level will be spaced at least one week apart (subjects 2, 3 and 4), with follow up at 1, 2 and 3 days post-injection for each subject prior to treatment of the next subject at that dose level. All subjects will receive injection of cells into the eye with the poorest visual acuity. Following at least one week of safety observations for the last study subject at the lower dose level, safety and tolerability data will be reviewed by the DSMB. Assuming no unexpected safety issues and with DSMB recommendation, an additional 4 subjects will be enrolled in Cohort 1 and treated at the second dose level, 1.0 x 10⁶ hRPC. Treatment will be similar to the first four subjects, i.e. intravitreal injection under topical anesthesia with treatment of the first two subjects separated by at least 4 weeks and subsequent subjects in this cohort (subject 6, 7 and 8) spaced at least one week apart. Following at least one week of safety observation for the last Cohort 1 subject, safety and tolerability data will be reviewed by the DSMB prior to initiation of Cohort 2.

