6.0 TREATMENT PLAN

6.1 Dose and Schedule

All subjects will receive a single intravitreal injection of hRPC at the assigned dose into the eye with the poorest visual acuity or, if vision is comparable in both eyes, the non-dominant eye. After topical anesthesia, a single 50 microliter suspension of cells (0.5, 1, 2 or 3 million) will be delivered under direct visualization into the vitreous cavity using a 30 g needle. This treatment does not require surgical detachment or manipulation of the retina. The injection procedure itself takes approximately 2 minutes. Following 60 minutes of observation with no serious clinical symptoms or manifestations (IOP < 30 mm Hg and vital signs comparable to pre-treatment), subjects will be released to home on the day of injection. Please refer to the study procedure manual for details of patient preparation and monitoring.

The schedule of observations and assessments during the study are summarized in Table 2.

jCyte, Inc Protocol No. JC-01

				I able A	2 Sche	aule of .	Assessm	ents (JC	Ĵ - 01)							
Timepoint	Scr	BL*	Day 0	Day 1	Day 2	Day 7 ⁷	Day 14 ⁷	Day 21 ⁷	Day 28 ⁷	M 2 ⁸	M3 ⁸	M4 ⁸	M5 ⁸	M6 ⁸	M9 ⁸	M12 or Early Term
Written informed consent	Х															
Medical history (MH)	Х	x*														Х
Physical examination (PE)	Х	x*														х
Brief MH and PE				х		Х			X		X			Х		
HLA typing	Х															
Weight	Х	x*	Х			Х										Х
Vital signs	Х	х	Х	Х	Х	х	Х	х	Х	Х	Х	Х	Х	Х	х	Х
Pregnancy test	Х	x*														х
Safety laboratory tests ¹	Х	x*				х			Х		Х			Х		Х
Infectious disease tests ²	Х	x*														
Urinalysis ³	Х	x*									Х			Х		х
Electrocardiogram	Х	x*	х	Х												
Slit lamp and fundus exam	Х	x ⁴		х	х	Х	Х	х	X	х	X	X	Х	Х	х	Х
BCVA (ETDRS)	Х	x	х	х	х	Х	Х	х	X	х	X	X	Х	Х	х	Х
ERG	x ⁹	x ⁹												Х		Х
IOP		x	х	х	х	Х	Х	х	X	х	X	X	Х	Х	х	Х
OCT		х							Х		Х			Х	х	Х
FA		х												x ⁶		х
AF		х												Х		х
VF (if applicable)		x												Х		Х
B-scan		х				Х					X			Х		Х
Exploratory non-invasive visual assessments (optional)		х									х			х	х	х
Study Drug Injection			х													
Con Meds			Х	х	х	х	х	х	х	х	х	х	Х	Х	Х	Х
Adverse events			х	х	х	х	х	х	х	х	х	х	Х	Х	Х	Х
Blood sample for Ab testing ⁵		х					Х		х							Х
Written consent for FU study																Х
		·				*	*	·					•			

 Table 2 Schedule of Assessments (JC -01)

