4. DETERMINATION OF SAMPLE SIZE

The sample size for this study was not based on any formal statistical considerations.

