10.1 Study Drug Administration

Treatment compliance will be assessed via direct observation by the study investigator who is responsible for study drug administration. The cell dose and exact time of injection will be recorded. Study drug administration responses will be tabulated for each treatment according to questions asked in the CRF, including whether the total dose was administered, whether there were any dose interruptions were there any AEs observed, were the subject's vital signs comparable to pre-treatment of study drug injection, was the subject's IOP measurement less than 30 mm post treatment of study drug injection and was the subject prescribed topical treatment after treatment of study drug injection.

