No	n (%)	n (%)	n (%)	n (%)	n (%)
Any Dose interruptions?					
Yes	n (%)	n (%)	n (%)	n (%)	n (%)
No	n (%)	n (%)	n (%)	n (%)	n (%)
Were any Adverse Events observed?					
Yes	n (%)	n (%)	n (%)	n (%)	n (%)
No	n (%)	n (%)	n (%)	n (%)	n (%)
Subject Vital Signs comparable to pre injection levels?					
Yes	n (%)	n (%)	n (%)	n (%)	n (%)
No	n (%)	n (%)	n (%)	n (%)	n (%)
Subject IOP < 30mm post treatment of injection?					
Yes	n (%)	n (%)	n (%)	n (%)	n (%)
No	n (%)	n (%)	n (%)	n (%)	n (%)
Subject Prescribed Topical Treatment after Study Drug					
Yes	n (%)	n (%)	n (%)	n (%)	n (%)
No	n (%)	n (%)	n (%)	n (%)	n (%)
cludes both Cohorts 1 and 2.					
gram.sas date time					

	Safety PopulationSafety PopulationCohort 1Cohort 2Class / rm $(N=)$ $(0.5 x 10^6 hRPC$ $(N=)$ $(N=)$ Total [1] $(N=)$ SubjectsEventsSubjectsEventsSubjectsEventsSubjectsEventsSubjectsEventsSubjectsEventsSubjectsEventsSubjectsEventsSubjectsEventsrting at Least One TEAEn (%)xxn (%)<									
		Coh	ort 1			Coh	ort2			
System Organ Class /	0.5 x 10	⁶ hRPC			0.5 x 10 ⁶	hRPC			Tota	ıl ^[1]
Preferred Term	(N=	=)	(N	=)	(N=	=)	(N	J=)	(N	=)
	Subjects	Events	Subjects	Events	Subjects	Events	Subjects	Events	Subjects	Events
Subjects Reporting at Least One TEAE	n (%)	XX	n (%)	XX	n (%)	XX	n (%)	XX	n (%)	xx
System Organ Class 1	n (%)	XX	n (%)	XX	n (%)	XX	n (%)	XX	n (%)	XX
Preferred Term 1	n (%)	XX	n (%)	XX	n (%)	XX	n (%)	XX	n (%)	XX
Preferred Term 2	n (%)	XX	n (%)	XX	n (%)	XX	n (%)	XX	n (%)	XX
System Organ Class 2	n (%)	XX	n (%)	xx	n (%)	XX	n (%)	XX	n (%)	XX
Preferred Term 1	n (%)	XX	n (%)	XX	n (%)	XX	n (%)	XX	n (%)	XX
Preferred Term 2	n (%)	XX	n (%)	XX	n (%)	XX	n (%)	XX	n (%)	XX

Table 14.3.1.1TEAEs by System Organ Class and Preferred TermSafety Population

^[1] Total includes both Cohorts 1 and 2.

...

Note: At each level of summation (overall, system organ class, preferred term), subjects reporting more than one adverse event are counted only once. path/t_program.sas date time

Table 14.3.1.2 TEAEs by System Organ Class, Preferred Term and Maximum Severity Safety Population

				Coh	nort 1			
System Organ Class /		0.5	x 10 ⁶ hRPC (N=)					
Preferred Term	Mild	Moderate	Severe	Life Threatening	Mild	Moderate	Severe	Life Threatening
Subjects Reporting at Least One TEAE	n (%)	n (%)	n (%)	n (%)	n (%)	n (%)	n (%)	n (%)
System Organ Class 1	n (%)	n (%)	n (%)	n (%)	n (%)	n (%)	n (%)	n (%)
Preferred Term 1	n (%)	n (%)	n (%)	n (%)	n (%)	n (%)	n (%)	n (%)
Preferred Term 2	n (%)	n (%)	n (%)	n (%)	n (%)	n (%)	n (%)	n (%)

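### The Day 0 IOP limit for release home is at most 30 mm Hg in Protocol 7.4 but below 30 mm Hg everywhere else, so the documents conflict at a reading of exactly 30 (minor inconsistency)

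*Protocol*

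**What the plan says.** The limit appears in two forms.

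- **30 allowed.** Protocol 7.4, item c of the list of steps after injection on Day 0: "intraocular pressure by tonometry post-treatment must be ≤30 mm Hg prior to patient release".
- **30 not allowed.** Protocol 3.1.1 makes release conditional, "based on intraocular pressure <30mm Hg and vital signs returned to pre-injection". The same condition stands in the synopsis for Cohort 1 and for Cohort 2, in Protocol 3.1.2, and in SAP section 3 for each cohort. Protocol 6.1 words it as "IOP < 30 mm Hg and vital signs comparable to pre-treatment), subjects will be released to home on the day of injection".

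The SAP also carries the strict form into the outputs. Section 10.1 lists the CRF questions to be tabulated, among them "was the subject's IOP measurement less than 30 mm post treatment of study drug injection". The study drug administration table shell in Appendix C has a Yes/No row, "Subject IOP < 30mm post treatment of injection", and the matching listing in Appendix D has a column on the same question.

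**The concern.** All these statements concern one decision: whether a subject may go home on the day of an intravitreal injection. They cannot be read as separate rules for separate times or cohorts, because the strict form is given for both cohorts and 7.4 applies to every subject. A site that follows 7.4 at a reading of 30 acts within that section and against 6.1. A monitor checking adherence to the protocol has no single standard for that reading.

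The SAP item inherits the problem. In the table shells it is the only tabulation of Day 0 IOP: the IOP summary shell goes from Baseline to Day 1 and on to later visits, with no Day 0 row. The Day 0 value itself is planned only for the IOP listing. Safety and tolerability is the primary objective, so the one summary of Day 0 pressure should match the rule under which subjects were released.

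**Working it through.** No sample-size, power or error-rate figure is involved; SAP section 4 says "The sample size for this study was not based on any formal statistical considerations". The check is a comparison of text, followed by a boundary check.

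**Count of statements of the release limit**

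- At most 30: Protocol 7.4 c, one statement.
- Below 30: synopsis Cohort 1, synopsis Cohort 2, Protocol 3.1.1, 3.1.2 and 6.1, SAP section 3 Cohort 1, SAP section 3 Cohort 2, seven statements.
- SAP output items asking about less than 30: section 10.1, the table shell and the listing column, three places.

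**Boundary check.** Apply x ≤ 30 and x < 30 to readings around the limit, taking the SAP item to refer to the reading shown.

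| IOP (mm Hg) | Release under 7.4 c (≤30) | Release under the other sections (<30) | SAP item (<30) | Conflict |
|---|---|---|---|---|
| 29 | yes | yes | Yes | no |
| 29.5 | yes | yes | Yes | no |
| 30 | yes | no | No | yes |
| 30.5 | no | no | No | no |
| 31 | no | no | No | no |

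The rules part at one value only.

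**Size in the table.** The documents give no frequency for a reading of exactly 30, so none is assumed. One such subject would be 1/28 = 3.6% of the Total column at the planned maximum of 28. In a single dose column the same subject would be 1/4 = 25.0% or 1/3 = 33.3%. Those larger figures are what any one subject contributes to a cell of that size and say nothing about how often the case arises.

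**Which reading the item means.** SAP 10.1 does not say. Take a subject who first reads 31 and later reads 29. Release at 29 is allowed under every section, yet the item is No if it records the first reading and Yes if it records the reading at release. Reconciling the limit alone would leave this open.

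**What depends on the limit.** The IOP safety criterion in Protocol 3.2.2 uses other values (a clinically significant, persistent rise of more than 10 mm Hg above baseline, or IOP above 25 mm Hg). The suspension rule in the synopsis and SAP section 3 uses CTCAE grades. Neither refers to 30 mm Hg.

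**The case against.** The strongest case on the other side is that this is a one-symbol mismatch with no analytic consequence. Most of that stands. Release does not rest on pressure alone: vital signs, absence of serious symptoms and a basic vision check are also required, and IOP, slit lamp and fundus are examined again on Day 1. No document says that 30 carries a different risk from 29. The study procedure manual, to which 6.1 refers sites, and the CRF are not available, so how sites applied the limit is unknown.

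Three stronger readings are tempting, and the documents support none of them.

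- **That a subject released at 30 is a recorded failure.** The item is a descriptive Yes/No. At 30, No is a correct answer to the question asked. The SAP does not label it a failure or deviation, and no endpoint or stopping consequence follows. It also reflects the release reading only if that is the reading recorded.
- **That 7.4 is the rule sites worked to and so overrides the rest.** Nothing ranks 7.4 above 6.1, which is the treatment plan and states the same condition.
- **That the effect on the safety table is 25 to 33%.** This is one subject divided by 4 or 3. The listing's two-digit placeholder for mean IOP is a display format and does not establish the resolution of the release reading.

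An artefact of text extraction is unlikely to explain the mismatch. The protocol uses both signs in the ordinary way elsewhere, and SAP 10.1 writes the strict limit in words.

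**Conclusion.** The inconsistency is real and minor. One section allows release at 30 mm Hg, seven other statements of the same condition do not, and nothing in either document settles which governs. The effect is confined to a reading of exactly 30. It touches a decision threshold for subject safety and one descriptive row, and leaves endpoints, stopping rules and sample size unaffected. This conclusion takes the printed signs as the sponsor's. The statement that the SAP item would be No for a subject released at 30 assumes that the item refers to the release reading, which the SAP does not say. Which limit is clinically right is not judged here.

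**What to change.** Reconcile every statement of the Day 0 release limit to one value chosen by the sponsor's medical lead: the synopsis (both cohorts), Protocol 3.1.1, 3.1.2, 6.1 and 7.4, and SAP section 3 (both cohorts). Match to it the question in SAP 10.1, the study drug administration table row, the listing column and the CRF question behind them. Add a short statement in SAP 10.1 of which post-injection reading the item uses, the first or the one at release.

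The cost depends on the choice. If only 7.4 changes, the limit itself is a one-character edit. If 7.4 stands, the other protocol sections, the SAP text, both shells and the CRF item need matching edits. If the CRF wording can no longer be changed, a footnote to the table could give the limit used for release and the reading that the item records. No analysis needs to be redesigned in either case.

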7.5 Follow up Visits

7.5.1 Day 1 (24 hours)

- a. brief medical history and physical exam, including any changes in vision or light perception reported by patient or noted by study staff not specifically assessed (for example, patient reports that general vision is "brighter" or study staff reports that patient response to certain assessments seems more rapid)
- b. vital signs
- c. ECG (24 hours post-injection)
- d. slit lamp and fundus exam
- e. BCVA
- f. IOP
- g. con meds
- h. adverse events

7.5.2 Day 2 (48 hours)

- a. vital signs
- b. slit lamp and fundus exam
- c. BCVA
- d. IOP
- e. con meds
- f. adverse events

7.5.3 Day 7 (week one)

- a. brief medical history and physical exam, including any changes in vision or light perception reported by patient or noted by study staff since prior H & PE
- b. weight
- c. vital signs
- d. CBC, platelet, differential, hemoglobin, hematocrit
- e. blood chemistries, not limited to, but must include AP, ALT, AST, BUN, Cr, total bilirubin, serum electrolytes, glucose, calcium, phosphate, albumin and total protein
- f. coagulation function, including PT/INR, PTT only participants who had abnormal values (out of normal range) at baseline
- g. slit lamp and fundus exam
- h. BCVA
- i. B-scan
- j. IOP
- k. con meds

l. adverse events

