Hematology (minimally Hct, Hgb, CBC with diff, plt), coagulation panel and blood chemistries (minimally AP, ALT, AST, BUN, Cr, total bilirubin, serum electrolytes, glucose, calcium, phosphate, albumin and total protein) ²Hepatitis B and C, HIV ³ Drug screen included at screening visit ⁴ Fundus photographs at baseline ⁵ Testing for Panel Reactive Antibodies (PRA) and Donor Reactive Antibodies (DRA) ⁶ Only if cystoid macular edema (CME) is observed on OCT ⁷ Visit window +/- 1 day ⁸ Visit window +/- 4 days ⁹ERG can be performed at screening to confirm eligibility; if so, does not need to be repeated at baseline. *Day -30 to 0. Does not need to be repeated if Day 0 is within 30 days of screening.

CONFIDENTIAL

22 of 41

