7.6 End of Treatment (Month 12) or Early Termination Visit

- a. MH and physical exam, including weight and height
- b. vital signs
- c. pregnancy test (if applicable)
- d. CBC, platelet, differential, hemoglobin, hematocrit

- e. blood chemistries, not limited to, but must include AP, ALT, AST, BUN, Cr, total bilirubin, serum electrolytes, glucose, calcium, phosphate, albumin and total protein
- f. coagulation panel, including PT/INR, PTT
- g. urinalysis
- h. slit lamp and fundus exam
- i. BCVA
- j. B-scan
- k. ERG
- 1. IOP
- m. OCT
- n. FA
- o. VF (if applicable)
- p. con meds
- q. adverse events
- r. blood sample for Ab testing
- s. exploratory visual assessments
- t. informed consent for follow-up study

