10.3 Clinical Laboratory Evaluation

Hematology, serum chemistry and coagulation laboratory parameters will be summarized using descriptive statistics at baseline, Day 7, Day 28, Month 3, Month 6, and Month 12/Early Term. Change from baseline in the laboratory parameters will also be presented, Unless otherwise noted, baseline is defined as the value obtained at the baseline visit. If the baseline value is missing, the baseline value will be the last nonmissing value recorded prior to the first dose of study drug.

No concerns are expected regarding the drug for laboratory results since the drug is expected to stay in the eye. As a result, no analysis using high/low flags will be carried out.

Urinalysis results will not be summarized but will be provided in data listing. Separate listing of abnormal clinically significant lab values and ECG interpretation will be presented.

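### The protocol disagrees with itself on who has coagulation tests between Day 7 and Month 6, and the SAP tabulates means and changes at those visits without noting that the subjects may be selected on baseline

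*Protocol*

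**What the plan says.** **Restricted reading.** Protocol 7.2 attaches a condition to the baseline coagulation test: "if abnormal at baseline, this test should be repeated each time standard safety labs, e.g. hematology and blood chemistries, are performed". Section 7.5.3 (Day 7) then limits PT/INR and PTT to "only participants who had abnormal values (out of normal range) at baseline", and the same restriction appears at Day 28 (7.5.6), Month 3 (7.5.8) and Month 6 (7.5.11). At Month 12 or early termination, Section 7.6 lists "coagulation panel, including PT/INR, PTT" with no restriction.

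**Unrestricted reading.** Table 2 marks safety laboratory tests at Day 7, Day 28, Month 3, Month 6 and Month 12. Its first footnote defines them as "Hematology (minimally Hct, Hgb, CBC with diff, plt), coagulation panel and blood chemistries", with no condition on baseline. Section 8.1.3 refers to Table 2 for the timing of laboratory samples and names PT/INR and PTT among the tests.

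**Analysis.** SAP 10.3 treats coagulation like hematology and chemistry: "coagulation laboratory parameters will be summarized using descriptive statistics at baseline, Day 7, Day 28, Month 3, Month 6", then Month 12 or early termination, with change from baseline as well. The shell of Table 14.3.4.3 shows n, mean (SD), median, minimum and maximum for PT, PTT and INR by cohort and dose level plus a total. No footnote says that the interim rows may come from a subset. SAP 8.3, placed in the efficacy section, imputes nothing, and Section 10 gives no imputation rule for laboratory values. SAP 10.3 also rules out any analysis by high/low flags.

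**The concern.** Under 7.2 and 7.5, the baseline result decides who is measured at the four interim visits. The same result is then subtracted to form the change from baseline. Two things follow.

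- The rows of one table describe different populations: everyone at baseline, only baseline-abnormal subjects from Day 7 to Month 6, and everyone again at Month 12. Reading down a column mixes selection with time.
- A value picked because it was extreme is expected to be less extreme on retest whether or not the product does anything, so a change toward normal in such a subject cannot be read as an effect.

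Safety is the primary objective and this is a planned safety table. A reader who sees only a small n has no means of knowing that those subjects were chosen for abnormal baselines.

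**Working it through.** **1. Who contributes to each row**

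| Row of Table 14.3.4.3 | Under Protocol 7.2, 7.5 and 7.6 | Under Table 2 footnote 1 and 8.1.3 |
|---|---|---|
| Baseline | all subjects | all subjects |
| Day 7, Day 28, Month 3, Month 6 | abnormal at baseline only | all subjects |
| Month 12/ET | all subjects | all subjects |

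The SAP table fits the right-hand column. Everything below applies only if the middle column describes what was done.

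**2. Denominator.** 2 cohorts × (4 + 4 + 3 + 3) = 28. This reproduces the protocol's planned maximum and gives eight cohort-by-dose columns, four with 4 subjects and four with 3.

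**3. Number retested.** The documents do not give the share out of range. Assume 5% per test, independent tests, and a repeat of the whole panel when any test is abnormal, which is how 7.2 and 7.5 read.

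| | Two effective tests (PT and INR overlap) | Three tests |
|---|---|---|
| Share retested | 1 − 0.95² = 9.75% | 1 − 0.95³ = 14.3% |
| Expected of 28 | 2.7 | 4.0 |
| Chance a 4-subject cell is empty | 0.9025⁴ = 66% | 0.8574⁴ = 54% |
| Chance a 3-subject cell is empty | 0.9025³ = 74% | 0.8574³ = 63% |

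At a rounded share of 15%, about 4.5 of the 8 columns are expected to be empty and about 0.7 to hold two or more subjects, the minimum for an SD. Over a wider assumed share of 5% to 30%, the expected number retested is 1.4 to 8.4.

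**4. Regression toward the centre.** Assume normally distributed values, selection above the upper 2.5% limit, test-retest correlation r of 0.5 to 0.9 (not in the documents) and no drug effect.

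- Mean baseline of those selected: φ(1.96)/0.025 = 2.34 SD above the centre.
- Expected change: −(1 − r) × 2.34.
- Expected value at the later visit: r × 2.34.

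| r | Expected change (SD) | Expected later value (SD from centre) | Back in range on retest |
|---|---|---|---|
| 0.5 | −1.17 | +1.17 | 81% |
| 0.7 | −0.70 | +1.64 | 67% |
| 0.9 | −0.23 | +2.10 | 41% |

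Simulation agreed with these changes to within 0.01 SD. If everyone is tested, the expected change is 0. For subjects selected high, the interim visit mean would lie above the all-subject baseline mean while the change row shows a fall. Two rows of one table would point in opposite directions with no effect present.

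**5. Direction of the column mean.** If a share h of the selected values is high and 1 − h is low, the expected mean change is −(2h − 1)(1 − r) × 2.34. With h = 1 this is the range above; with h = 0.5 it is 0. The documents do not give h. A test repeated only because another test was abnormal regresses only through the correlation between the two.

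**The case against.** The strongest reply is that the selection may never have happened. Table 2 footnote 1 and Section 8.1.3 call for coagulation without restriction; if sites worked from these, the SAP table is correct. That stands, and it makes the statistical artefact conditional. The protocol's self-contradiction is not conditional.

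A reader might infer that the tabulated mean change is biased toward normalisation by construction. The documents do not support this. The drift holds for each selected out-of-range value, but highs and lows can cancel in a mean, and neither direction nor share is given. A reader might also take 5% for one test and conclude that 81% to 86% of cells (0.95⁴ to 0.95³) would be empty. That uses the wrong unit, because the repeat rule appears to cover the panel.

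The harm is limited. The shell prints n at each visit, Listing 16.2.8.3 shows PT, PTT and INR by subject and visit, and Listing 16.2.8.5 collects clinically significant values. There is no hypothesis test, no coagulation mean enters the suspension rule, and the sponsor expects no laboratory concern because the product should stay in the eye. A reading that the table undermines the safety conclusions therefore goes too far. These safeguards still do not tell the reader how the interim subjects were chosen.

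**Conclusion.** The point holds and is minor. Two facts rest on the text alone: the protocol gives two incompatible rules for interim coagulation testing, and the SAP tabulates means and changes at those visits with no note of selection. If 7.2 and 7.5 governed, the interim rows describe a small baseline-selected group placed between two all-subject rows.

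The drift for a value selected as high, about 0.2 to 1.2 SD, rests on normality and the assumed correlations. The count of about 3 to 4 of 28 retested, with 54% to 74% of cells empty, rests on the assumed 5% per test, independence and panel-wide retesting. The sign and size of the bias in any column mean cannot be determined and may be zero. The Month 12 summary covers everyone and is not affected.

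**What to change.** 1. Reconcile Table 2 footnote 1 and Section 8.1.3 with Sections 7.2 and 7.5. If testing is already complete, state in the SAP which rule the sites applied.
2. If the restriction stands, limit the all-subject summary in Table 14.3.4.3 to baseline and Month 12/ET, and present Day 7 to Month 6 results per subject in Listing 16.2.8.3. An acceptable alternative is separate rows labelled as baseline-abnormal subjects only, with no pooled change from baseline.
3. If all subjects were tested, keep the table as planned.

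On the SAP side the cost is one sentence plus some removed or relabelled rows in one table. SAP Appendices A and B already allow tables to be reorganised during programming. No data are lost, since interim results remain in the listing.
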